HEMATOLOGY: ***[name], [name], [name], [name], [name], [name], [name], [name], [name]**

*Eligible to obtain informed consent

A Comprehensive Cancer Center Designated
by the National Cancer Institute

Phase: II

YCC Version 4.0 Date: 31-May-2017

pg. 5

Table of Contents

1. Protocol Synopsis.....	6
2. Schedule of Study	
Assessments.....	10
3. Background and Rationale	11
4. Study Objectives and End Points	14
5. Investigational Plan.....	14
6. Serious Adverse Events.....	18
7. Protocol Amendments and Deviations.....	19
8. Data Management.....	19
9. Biostatistical Considerations.....	20
10. References.....	23
11. Appendices.....	25
A. Correlative Studies and collection of research samples	

Protocol Synopsis

PROTOCOL SUMMARY: A Randomized, Placebo-Controlled Study utilizing high dose trivalent influenza vaccine dose with a booster compared to standard of care in patients with monoclonal gammopathies

STUDY INTERVENTION:	Fluzone® High-Dose vaccine with a 30 day booster dose
INDICATION:	All patients with a diagnosis of a monoclonal gammopathy
STUDY Type:	Randomized, double blind, placebo-controlled, Phase II Study

Background and Rationale:

Influenza is a major cause of morbidity in the US. Patients with monoclonal gammopathies are known to have increased risk of developing influenza. Furthermore, several of the medications (such as proteasome inhibitors), commonly used to treat these tumors, are known to further increase the risk of these tumors. Seasonal influenza vaccination has been shown to reduce influenza related morbidity and is approved for routine prophylaxis in US. In 2009, Fluzone® high-dose vaccine was FDA approved in 2009 for adults aged 65 and older based on the data regarding higher rates of seroprotection (defined as hemagglutination antibody inhibition (HAI) titer of 40 or higher).

Sensing of pathogens by the immune system is mediated by family of distinct pattern recognition receptors (such as toll like receptors, TLRs) that then activate immune response. In the setting of tumors involving the immune cells themselves, such as multiple myeloma, tumor cells commonly express TLRs and signaling via TLRs has been shown to regulate the growth and survival of tumor cells. This has led to the hypothesis that exposure to common pathogens may itself contribute to promoting the growth of tumor cells. Unfortunately, these patients also have immune paresis and are at increased risk for infections. Prevention of major seasonal infections may therefore have major impact not only on infection-related morbidity, but also tumor growth. In addition to potentially direct effect on tumor cells, pathogen-related morbidity also leads to interruption of therapy, which may further compromise disease control. Thus, influenza infections may cause mortality directly or indirectly by interfering with disease control. By measuring all-cause mortality at the end of an influenza season it is possible to account for all possible effects of influenza which may be related to mortality.

Although seasonal influenza vaccination is routinely employed in patients with monoclonal gammopathies, the data about its efficacy in this setting are limited and very few studies have specifically focused on this population. This is particularly true in the setting of newer agents that further reduce B cell function. Existing data suggest that routine seasonal influenza vaccination is not very effective in this population, with seroconversion rates of <20%. One approach to enhancing the efficacy of vaccination is the use of boosters. In the past 2013-2014 flu season, Hahn et al gave a standard dose influenza booster vaccine after 30 days to 25 myeloma patients and noted a doubling of serologic protection (HAI titer ≥ 40) from 14% to 33%. This suggests that

A Comprehensive Cancer Center Designated
by the National Cancer Institute

Phase: II

YCC Version 4.0 Date: 31-May-2017

pg. 7

there may be a role for booster vaccines in these patients, however there is much room to improve. Although routinely used in adults 65 and older, there are no prospective data on high dose flu vaccine (and specifically booster) in patients with monoclonal gammopathies. Fluzone® High-Dose has been widely used since 2009 and proven to be safe. Knowing that high dose influenza vaccine increases serologic protection in adults over 65, there is a chance that our study population may benefit as well with a booster strategy including the high dose vaccine.

We recently concluded a pilot study at Yale-New Haven Hospital over the 2014-2015 influenza season, (the SHIVERING Trial), using the same proposed high dose influenza vaccine with booster strategy. While much of the data analysis (including correlative studies of immune response) is currently ongoing, preliminary findings reveal that this strategy was safe and well tolerated in this population. All 51 patients who were enrolled received both high dose vaccine and booster doses and there were no grade 2 or above adverse events attributed to the study vaccine. In addition flu infection rate was only 4% of patients compared to an expected rate of 20% in this population. The findings from the pilot study, if confirmed in the context of a randomized controlled trial as proposed here, therefore have practice changing implications for the care of patients with monoclonal gammopathies / myeloma.

Our hypothesis is that the administration of Fluzone® High-Dose with booster to all patients with monoclonal gammopathies (irrespective of age) will lead to seroconversion rates exceeding 50% and more importantly, will reduce influenza-related morbidity, reduce interruptions in cancer therapy and reduce all-cause mortality at the end of the flu season.

In this study, we will administer Fluzone® High-Dose vaccine with a planned booster to patients with monoclonal gammopathies irrespective of age versus a standard of care control group. Primary endpoint is composite of documented influenza infection rate and disease progression (as defined by International Myeloma Working Group criteria) at the end of the flu season. Based on the background data, we expect a higher rate of success in the experimental arm. As such, we power for success rates of 90% and 70% in the experimental and control arms, respectively. We will also analyze several secondary endpoints including rates of influenza related morbidity, the analysis of humoral and cellular immune response to these vaccines and the rate of disease control (defined as lack of disease progression by standard international myeloma working group criteria).

By comparing this experimental approach directly to standard of care, data from estimates of effectiveness will inform the design of larger future controlled studies. As such, the data from this study can lead to practice-changing results. The data on immune correlates will also yield important information about *in vivo* "immune-competence" of these individuals, which in turn is important to design trials with emerging immune therapies.

STUDY Endpoints:

Primary:

- 1) The primary clinical endpoint of this study is: to measure a composite of documented influenza infection rate and disease progression (as defined by International Myeloma Working Group criteria) at the end of the flu season following a high dose influenza vaccine booster strategy versus standard of care.

A Comprehensive Cancer Center Designated
by the National Cancer Institute

Phase: II

YCC Version 4.0 Date: 31-May-2017

pg. 8

Secondary:

1. evaluate rates of serologic protection (defined as HAI titer >40) following Fluzone® High-Dose influenza vaccine with booster dosing versus standard of care.
2. measure T cell subsets and flu-specific T cell responses following high dose influenza vaccine booster dosing strategy versus standard of care.

STUDY DESIGN:

This is a phase II randomized placebo-controlled interventional study. Patients will be randomized in a 2:1 allocation of experimental group A to standard of care group B. Experimental group will receive high dose influenza vaccine with a booster high dose flu vaccine one month later. Standard of care arm will receive a single influenza vaccine (standard dose if age <65 and high dose if age \geq 65) and a placebo booster vaccine after one month. Both group A and B will be stratified by disease type to allow for a balanced study population. Patients can be viewed as two distinct populations, those with disease requiring therapy (defined as any plasma cell disorder having at any time required therapy) and those with early disease (defined as asymptomatic multiple myeloma, asymptomatic Waldenstrom macroglobulinemia, or monoclonal gammopathy of undetermined significance). As such, we will stratify patients by disease requiring therapy versus early disease by separately randomizing patients into the two protocol groups but with the same allocation ratio of 2:1. Patients treatment is summarized as follows:

Group (Each group stratified by disease requiring therapy and early disease)	Randomization	Initial Influenza Vaccine at day 0	Second High Dose Influenza Vaccine at day 30 (+14 days/-7days)
Experimental (A)	2	Fluzone® High-Dose	Fluzone® High-Dose
Standard of Care (B)	1	Fluzone® High-Dose if age \geq 65, Standard dose influenza vaccine if age < 65.	Placebo

A Comprehensive Cancer Center Designated
by the National Cancer Institute

Phase: II

YCC Version 4.0 Date: 31-May-2017

pg. 9

STUDY DURATION: 2015-2016 influenza season	TOTAL SAMPLE SIZE: 150 Subjects (100 in experimental group A and 50 in standard of care group B)
DOSING REGIMEN: Fluzone® High-Dose trivalent inactivated influenza vaccine given on day 0 and again on month +1 (+14 days/-7 days) in the experimental group.	

Schedule of Study Assessments

Procedure	2015 – 2016 Flu Season (August to May)				
	Day of Initial Vaccine (Fluzone High Dose in experimental group A vs. standard of care in group B) Day of Initial vaccine, study enrollment and randomization into experimental versus standard of care arm	Day 7 (+/- 2 days) Research blood draw only*	Day of Second Vaccine (Fluzone High Dose in experimental group A vs. placebo booster in group B) Roughly 30 Days following Initial vaccine (+21 days/- 7 days)	Month 2 Roughly 30 Days following Second Vaccine (+14 days/- 7 days)	End of Study Visit ⁴ (may be conducted in person, by telephone, or by email) (End of flu season-May 1 to May 15, 2016)
SPEP OR IFE OR serum free light chains OR quantitative immunoglobulins ¹	X				X
Research blood draw ²	X	*X (patients may refuse this blood draw if it creates an unacceptable burden)	X	*X (if patients are unable to receive this blood draw within the above timeframe, blood draw may be delayed up to 90 days)	*X (patients may refuse this blood draw if it creates an unacceptable burden)
Inquire and document any influenza infection ³ , influenza-related hospitalization, or death during the study period	X		X	X	X
Assessment of all grade II and above adverse events ⁵			X	X	
Pregnancy test for women of childbearing potential ⁶	X		X		

¹ Assessment of disease status within 30 days prior to first vaccine and within 90 days of the End of Study Visit. Both patients with measurable or evaluable disease are eligible. The preferred method to monitor disease should be established at baseline and repeated at the end of study visit. For patients with measurable disease, SPEP or FLC are preferred.

² See Appendix A for details regarding collection of research samples and correlative studies.

³ All subjects should be informed and reminded to present to a health care facility at the first symptoms of possible influenza infection to have DFA checked.

⁴ End of treatment and 30 days following second vaccine may be merged into a single visit if they fall within 15 days of each other.

⁵ See Adverse Events section of the protocol for details.

⁶ Childbearing potential is defined as a sexually mature woman who 1) has not undergone a hysterectomy or bilateral oophorectomy and 2) has not been post menopause for at least 24 months. Pregnancy test to be performed within 2 weeks prior to each vaccine.

A Comprehensive Cancer Center Designated
by the National Cancer Institute

Phase: II

YCC Version 4.0 Date: 31-May-2017

pg. 11

Background and Rationale

Introduction

Plasma cell dyscrasias or monoclonal gammopathies are a group of benign and malignant disorders consisting of monoclonal plasma cells which secrete monoclonal immunoglobulins¹. These disorders include the pre-malignant entity Monoclonal Gammopathy of Undetermined Significance (MGUS), asymptomatic / active multiple myeloma, asymptomatic / active Waldenström Macroglobulinemia (WM), solitary plasmacytoma, and primary amyloidosis. Patients with monoclonal gammopathies are routinely offered influenza vaccines however there is no evidence that they are effective in preventing infections.

Influenza Vaccination

Influenza is a major cause of morbidity in the US. The most vulnerable populations include adults over the age of 65 years, those with serious co-morbidities². A particularly vulnerable population are thought to be patients with hematologic malignancies, particularly multiple myeloma. A population based study in Sweden of over 9,000 myeloma patients, demonstrated that myeloma was associated with a 5.4 fold increased risk of contracting influenza infections relative to healthy controls³.

Clearance of viral infection and vaccine responses are dependent on cell mediated immunity(CMI). The most accepted serologic measurement of antibody protection following influenza vaccine administration is hemagglutination antibody inhibition (HAI) titer of 40 or higher. However, this cutoff corresponds to an estimated 50% clinical benefit of preventing influenza infections, based on studies in young healthy adults^{4,5}. It is believed that CMI declines with age, which may help explain why the elderly are more vulnerable to influenza infections. HAI titers have also been shown to be lower in the elderly compared to young adults⁶. Based on studies showing increased serologic protection, Fluzone® high-dose vaccine was FDA approved in 2009 for adults aged 65 and older.

Patients with plasma cell dyscrasias are known to have depressed immune function. Studies in myeloma have shown B cell dysfunction (hypogammaglobulinemia), functional abnormalities of dendritic and T cells, inversion of T cell CD4:CD8 ratio, abnormal T cell Th1/Th2 CD4⁺ ratio, and dysfunction of natural killer cells^{7,8,9}. Anti-cancer medications can further adversely affect the immune system. It is known that patients who received chemotherapy within 7 days of trivalent inactivated influenza vaccine have poorer responses¹⁰. There is no published data regarding the effects of more commonly used novel agents such as IMIDs and proteasome inhibitors on vaccine responses.

Several studies have demonstrated a poor serologic antibody response in those patients included with myeloma and WM. However, there is a paucity of prospective trials focusing exclusively on patients with monoclonal gammopathies. No studies have specifically investigated influenza

A Comprehensive Cancer Center Designated
by the National Cancer Institute

Phase: II

YCC Version 4.0 Date: 31-May-2017

pg. 12

immunity in precursor states such as MGUS, although these patients may have similar risks of unresponsiveness to influenza vaccine and are known to have hypogammaglobulinemia. Based on available trial data restricted to myeloma patients, serologic protection (HAI titer ≥ 40) to all three influenza strains following trivalent influenza vaccine is achieved in less than 20% of myeloma patients in each trial^{11, 12, 13}. There have been two trials investigating the benefit of booster vaccine in myeloma patients. In 2005 Ljungmen et al, studied 70 patients with hematologic malignancies (10 with myeloma and 4 with WM) and administered a booster dose 30 days following standard influenza vaccine booster and found no increase in serologic protection¹⁴. More recently, in the past 2013-2014 flu season, Hahn et al gave a standard dose influenza booster vaccine after 30 days to 25 myeloma patients and noted a doubling of serologic protection (HAI titer ≥ 40) from 14% to 33%¹⁵. This suggests that there may be a role for booster vaccines in patients with hematologic malignancies, however there is obviously much room to improve.

Although routinely used in adults 65 and older, no one had studied high dose flu vaccine specifically in patients with monoclonal gammopathies. Fluzone® High-Dose has been widely used since 2009 and demonstrated to be safe. Knowing that high dose influenza vaccine increases serologic protection in adults over 65, our study population may benefit as well, given the similar but more significantly depressed cellular immunity in patients with monoclonal gammopathies. With this in mind, we have already designed the recent SHIVERING Pilot study at Yale New Haven Hospital over the 2014-2015 flu season. In this pilot study, all patients received Fluzone® High-Dose with a second booster dose after 30 days. Enrollment has closed and data analysis is ongoing. However, preliminary data revealed that all 51 patients enrolled tolerated the two vaccine doses well and no grade 2 or above adverse events related to vaccine were reported. In addition, with very close follow-up 2/51 patients (4%) patients developed documented flu infections despite an expected rate of 20% in this population (manuscript in preparation).

Rationale for Treatment in this Setting

Sensing of pathogens by the immune system is mediated by family of distinct pattern recognition receptors (such as toll like receptors, TLRs) that then activate immune response. In the setting of tumors involving the immune cells themselves, such as multiple myeloma, tumor cells commonly express TLRs and signaling via TLRs has been shown to regulate the growth and survival of tumor cells. For example, infectious particles can activate TLRs and cause proliferation of myeloma cell lines and secretion of IL-6 (a potent myeloma growth cytokine)¹⁶. This has led to the hypothesis that exposure to common pathogens may itself contribute to promoting the growth of tumor cells. Unfortunately, these patients also have immune paresis and are at increased risk for infections. Prevention of major seasonal infections may therefore have major impact not only on infection-related morbidity, but also tumor growth. In addition to potentially direct effect on tumor cells, pathogen-related morbidity also leads to interruption of therapy, which may further compromise disease control.

A Comprehensive Cancer Center Designated
by the National Cancer Institute

Phase: II

YCC Version 4.0 Date: 31-May-2017

pg. 13

Ultimately if this novel vaccine strategy proves to be more effective, an important question will be if mortality will also be improved. As discussed above influenza infections are associated both with their own morbidity and mortality, and may have a negative impact on disease control, thereby indirectly increasing mortality. All-cause mortality as a clinical endpoint will take into account all possible relation of influenza infections to mortality. One year estimates are known for patients with plasma cell disorders. The most recent SEER data of one year survival for newly diagnosed myeloma, based on patients diagnosed in 2009 is 79.2%.¹⁷ Relapsed refractory patients have lower survival depending on many risk factors and is estimated as low as 60-66%.^{18,19} MGUS patients are not believed to have much of a decrease in survival compared to age-matched controls and one-year survival is estimated to be 98%.²⁰ Most of the patients seen at Smilow cancer Hospital are relapsed/refractory multiple myeloma patients. We anticipated that more than 2/3 of patients enrolled will be relapsed / refractory and less than 1/3 will be MGUS or newly diagnosed plasma cell disorder patients. As would be expected, relapsed patients have reduced time to progression with each successive line of therapy. Kumar, et al²¹ followed 355 myeloma patients who have had at least two lines of therapy and showed that time to progression shortened with each line of therapy from 9.9 months after first therapy to 7.3 months after second therapy to less than 4 months after sixth line of therapy (see Figure 1 below). In our population of patients of relapsed patients mixed with newly diagnosed and early disease patients a conservative estimate of the proportion who would relapse from the time of initial vaccine to the end of the influenza season (which may range from roughly 4-8 months depending on when the patient receives their initial vaccine) is 10%. Considered together with an expected influenza infection rate of 20%, we would expect our control arm to have a combined disease progression and influenza infection rate of 30% (10%+20%).

To the authors' knowledge, there have not been any prior influenza vaccine studies in patients with monoclonal gammopathies, which have looked at clinical endpoints other than our pilot SHIVERING trial. Clinical endpoints which we plan to assess include number of influenza infections, influenza-related hospitalizations / deaths, and efficacy related to prior therapy. While prior studies have measured serologic response to influenza vaccines in patients with monoclonal gammopathies, there have not been any trials correlating T cell responses. We plan to try to better understand cell mediated immunologic response by looking at T cell functional assays.

Our **hypothesis** is that the administration of Fluzone® High-Dose with booster to all patients with monoclonal gammopathies (irrespective of age) will lead to seroconversion rates exceeding 50% and more importantly, will reduce influenza-related morbidity, prevent interruptions in cancer therapy and reduce disease progression at the end of the influenza season.

In this study, we will administer Fluzone® High-Dose vaccine with a planned booster to patients with monoclonal gammopathies (randomized into the experimental group versus standard of care). The experimental group will receive Fluzone® High-Dose vaccine with a second booster dose after 30 days, regardless of age. In the standard of care group, patients will receive influenza vaccine based on current standard of care clinical practice. Standard of care depends on age; patients ≥ 65 receive a single high dose influenza vaccine, patients < 65 receive a single

A Comprehensive Cancer Center Designated
by the National Cancer Institute

Phase: II

YCC Version 4.0 Date: 31-May-2017

pg. 14

standard dose vaccine. In addition, patients in the standard of care group will receive a placebo vaccine after 30 days, which will aid in the blinding between groups and allow for stricter comparison between groups.

Primary endpoint is a composite of documented influenza infection rate and disease progression (as defined by International Myeloma Working Group criteria) at the end of the flu season. We will also analyze several secondary endpoints including rates of influenza related morbidity, analysis of humoral and cellular immune response to these vaccines, and rate of disease control (defined as lack of disease progression by standard international myeloma working group criteria).

By comparing this experimental approach directly to standard of care, data from estimates of effectiveness will inform the design of larger future controlled studies. As such, the data from this study can lead to practice-changing results. The data on immune correlates will also yield important information about in vivo “immune-competence” of these individuals, which in turn is important to design trials with emerging immune therapies.

Study Objectives

Endpoints

Primary endpoints

The primary clinical endpoint of this study is to measure a composite of documented influenza infection rate and disease progression (as defined by International Myeloma Working Group criteria) at the end of the flu season following a high dose influenza vaccine booster strategy versus standard of care. Please see sections under biostatistical considerations for details.

Secondary study endpoints

The secondary endpoints are 1) rates of serologic protection (defined as HAI titer >40) following Fluzone® High-Dose influenza vaccine after booster dosing and 2) measurement of T cell subsets and flu-specific T cell responses.

Investigational Plan

Study vaccine description

Fluzone® High-Dose

A Comprehensive Cancer Center Designated
by the National Cancer Institute

Phase: II

YCC Version 4.0 Date: 31-May-2017

pg. 15

Proper Name: Influenza Virus Vaccine

Trade Name: Fluzone® High-Dose Vaccine

Manufactuer: Sanofi Pasteur, Inc, License #1725

Indication: Fluzone High-Dose is indicated for active immunization of persons 65 years of age and older against influenza disease caused by influenza virus subtypes A and type B contained in the vaccine.

Fluzone (Influenza Virus Vaccine) for intramuscular injection is an inactivated influenza virus vaccine, prepared from influenza viruses propagated in embryonated chicken eggs. The virus-containing allantoic fluid is harvested and inactivated with formaldehyde. Influenza virus is concentrated and purified in a linear sucrose density gradient solution using a continuous flow centrifuge. The virus is then chemically disrupted using a nonionic surfactant, Octylphenol Ethoxylate (Triton®X-100), producing a “split virus”.

The split virus is further purified and then suspended in sodium phosphate buffered isotonic sodium chloride solution.

Fluzone is standardized according to United States Public Health Service requirements and is formulated to contain HA of each of the following three influenza strains recommended for the current influenza season, including two A subtypes (H3N2 / H1N1) and one influenza B subtype.

Dosage form

Fluzone® High Dose is supplied in 0.5 mL for intramuscular injection

Adverse events:

In adults 18 through 64 years of age, the most common injection-site reaction was pain (>50%); the most common solicited systemic adverse events were headache and myalgia (>30%).

In adults >65 years of age, the most common injection-site reaction was pain (>20%); the most common solicited systemic adverse events were headache, myalgia, and malaise (>10%).

Post Marketing Experience

The following events have been spontaneously reported during the post-approval use of Fluzone.

- Blood and Lymphatic System Disorders: Thrombocytopenia, lymphadenopathy.
- Immune System Disorders: Anaphylaxis, other allergic/hypersensitivity reactions (including urticaria, angioedema)
- Eye Disorders: Ocular hyperemia

A Comprehensive Cancer Center Designated
by the National Cancer Institute

Phase: II

YCC Version 4.0 Date: 31-May-2017

pg. 16

- Nervous System Disorders: Guillain-Barré syndrome (GBS), convulsions, febrile convulsions, myelitis (including encephalomyelitis and transverse myelitis), facial palsy (Bell's palsy), optic neuritis/neuropathy, brachial neuritis, syncope (shortly after vaccination), dizziness, paresthesia
- Vascular Disorders: Vasculitis, vasodilatation/flushing•
- Respiratory, Thoracic and Mediastinal Disorders: Dyspnea, pharyngitis, rhinitis, cough, wheezing, throat tightness
- Skin and Subcutaneous Tissue Disorders: Stevens-Johnson syndrome
- General Disorders and Administration Site Conditions: Pruritus, asthenia/fatigue, pain in extremities, chest pain
- Gastrointestinal Disorders: Vomiting

Screening and Eligibility

The Investigator is responsible for keeping a record of all subjects who sign an Informed Consent Form for entry into the study. All subjects will be screened for eligibility. Screening procedures are outlined in Section 2, Schedule of Study Assessments and may take place on or < 30 days before the day of first vaccine administration.

Approximately 150 of subjects with monoclonal gammopathies will be screened for enrollment and must meet the eligibility criteria below. 100 patients will be randomized into the experimental group and 50 subjects will be randomized into the standard of care group. During screening, patients will be identified by disease type as having either disease requiring therapy or early disease. In order to maintain balanced stratification, patients of each disease type will be separately allocated in the same ratio of 2:1 experimental to control group. If a patient dies or discontinues their participation for any reason, we will not add another patient in their place.

Inclusion Criteria

Subjects must meet the following inclusion/exclusion criteria to be eligible for the study.

Inclusion criteria

1. Understand and voluntarily sign an informed consent form.
2. Age \geq 18 years at the time of signing the informed consent form.
3. Diagnosis of any monoclonal gammopathy: Monoclonal Gammopathy of Undetermined Significance (MGUS), asymptomatic / active multiple myeloma, asymptomatic / active Waldenström Macroglobulinemia (WM).

Exclusion criteria

1. Any serious egg allergy or prior serious adverse reaction to an influenza vaccine.

A Comprehensive Cancer Center Designated
by the National Cancer Institute

Phase: II

YCC Version 4.0 Date: 31-May-2017

pg. 17

2. Use of any other influenza vaccine for the 2015 to 2016 flu season.
3. Women who are pregnant or plan to become pregnant in the study period.

Visit schedule and assessments

Screening Assessments and all on study scheduled visits and assessments are outlined in Section 2 Table of Study Assessments.

At the end of the 2015-2016 flu season between May 1 to May 15, subjects will undergo off study evaluations per the Schedule of Assessments.

Vaccine Administration

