Appendix A – Correlative Studies and Collection of Research Samples

Timing:

Blood:

30 ml in heparin anticoagulant (4 green tops)

- Day of first vaccine \pm 1 week
- 7 Days after first vaccine \pm 2 days (optional)
- Day of second vaccine \pm 1 week
- 30 Days after second vaccine (-1 week, + 90 days)
- End of study blood draw between May 1 to May 15, 2016 (optional)

[figure not shown]
Correlative studies:

The [name] lab will process the research samples for performance of the following assays:

- Measurement of T cell subsets, including CD4+/CD8+, NK cells (Flow cytometry)
- Influenza-specific T cell response (intracellular cytokine analysis)
- HAI titers for influenza A and B
- Temporarily freeze PBMCs for cell mediated immune studies. Samples will be destroyed of after all testing is completed and the study is closed.

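### The only HAI endpoint defined is the rate above one cut-off: add a per-strain, baseline-adjusted titer comparison, and settle >40 versus 40 or higher

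*Combined protocol and SAP*

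**What the plan says.** The Synopsis sets the first secondary endpoint as: "evaluate rates of serologic protection (defined as HAI titer >40) following Fluzone® High-Dose influenza vaccine with booster dosing versus standard of care". Section 4 (Study Objectives, secondary endpoints) gives the same dichotomy, without naming the comparator: "rates of serologic protection (defined as HAI titer >40) following Fluzone® High-Dose influenza vaccine after booster dosing".

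The Synopsis and the Rationale also promise an "analysis of humoral and cellular immune response to these vaccines", but neither says what it will consist of. Biostatistical Considerations does not mention HAI. No geometric mean titer, fold rise, log-titer model or baseline adjustment appears anywhere.

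Appendix A lists "HAI titers for influenza A and B" among the assays. Blood is drawn around the first vaccine, around the second vaccine and about 30 days after the second, with two further optional draws.

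On the cut-off, the Influenza Vaccination section says the most accepted serologic measure of protection is an "hemagglutination antibody inhibition (HAI) titer of 40 or higher". It then qualifies this: "this cutoff corresponds to an estimated 50% clinical benefit of preventing influenza infections, based on studies in young healthy adults". The Synopsis background and the cited myeloma results also use 40 or higher, whereas both statements of the endpoint use a strict >40.

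**The concern.** A rate at one cut-off treats a rise from below 10 to 20, or from 80 to 640, as no change. The endpoint also makes no use of the pre-vaccination titer. The protocol itself traces the 50% benefit at this cut-off to young healthy adults, and then describes marked immune dysfunction in its own population. That weakens the case for letting the cut-off carry the whole serologic comparison.

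What is at stake is the precision of a secondary comparison that the protocol wants to use in designing later trials. Modest contrasts are plausible. Patients aged 65 or over receive the high-dose vaccine first in both arms, so for them only the second injection differs. One of the two booster studies cited found no increase in serologic protection.

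The endpoint is also incompletely defined. If titers are read on a doubling scale through 40, a strict >40 means 80 or higher. It is not stated whether the rate applies per strain or to all strains together, or at which visit.

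**Working it through.** **No figure to reproduce.** The plan gives no power, SD or sample-size figure for HAI, so everything below is illustrative.

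**Inputs from the documents.** There are 50 control and 100 experimental patients. Seroprotection to all three strains after standard vaccine "is achieved in less than 20% of myeloma patients in each trial". The rate went from 14% to 33% in the cited standard-dose booster study. The hypothesised rate with the new strategy exceeds 50%, although the protocol calls this seroconversion, a term it does not define.

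**Assumptions.** Log titers are normal with equal SD, the vaccine shifts every patient by the same amount, and no samples are missing. Two-sided 0.10 is also assumed: the plan gives 0.1 for the primary endpoint only and does not state sidedness.

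**Information kept by a cut-off.** With proportion p above the cut-off and z the matching normal quantile, relative efficiency = φ(z)² / [p(1 − p)].

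| p | φ(z) | p(1 − p) | Efficiency | Loss |
|---|---|---|---|---|
| 0.50 | 0.399 | 0.250 | 0.637 | 36% |
| 0.33 | 0.362 | 0.221 | 0.593 | 41% |
| 0.20 | 0.280 | 0.160 | 0.490 | 51% |
| 0.14 | 0.223 | 0.120 | 0.411 | 59% |

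Real titers are coarse and have a floor. With doubling dilutions, a floor at <10 and a log2 SD of 1.5–2.5 (all assumed), the loss over p = 0.14–0.50 is about 31–52% for a cut-off of ≥40 and 34–56% for >40. Taken together, the range is roughly 31–59%.

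**Power for 20% versus 35%, two-sided 0.10** (a contrast chosen for illustration).

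- Rates: the pooled rate is (50 × 0.20 + 100 × 0.35)/150 = 0.30. The null SE is √(0.30 × 0.70 × 0.03) = 0.0794 and the alternative SE is √(0.16/50 + 0.2275/100) = 0.0740. Then (0.15 − 1.645 × 0.0794)/0.0740 = 0.26, which gives power 0.60. Exact enumeration of the pooled z test gives 0.61.
- Log titers: the shift is d = z(0.35) − z(0.20) = 0.456 SD. Dividing by √(1/50 + 1/100) = 0.173 gives 2.63, and noncentral-t power is 0.84. With doubling dilutions and a floor it is about 0.75–0.80.

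**Other contrasts** (continuous log titers, two-sided 0.10).

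| Control vs experimental | Rates | Log titers |
|---|---|---|
| 14% vs 33% | 0.83 | 0.98 |
| 20% vs 33% | 0.51 | 0.75 |
| 20% vs 50% | 0.98 | 0.999 |

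At two-sided 0.05, the 20% versus 50% contrast already has power 0.96 on rates, against 0.998 on log titers.

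**A different mechanism.** Suppose the vaccine changes only the share of responders, 20% versus 40%. Responders average 3.5–4 and non-responders −1 to 0 on log2(titer/10), all assumed. On the floored dilution scale, power at two-sided 0.10 is then about 0.75–0.81 on rates and 0.71–0.79 on log titers, so the advantage disappears or slightly reverses.

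None of these figures includes the gain from adjusting for the baseline titer. The documents give no correlation from which to estimate it.

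**The case against.** The strongest case on the other side is that the loss is a property of an assumed model and not of this trial. The documents give no titer SD or distribution. In a population with immune paresis, a vaccine that turns some non-responders into responders is as plausible as one that shifts everyone, and the rate then does as well or slightly better. At the protocol's own contrast, rates already have ample power. The figure of less than 20% is for all three strains together; each single-strain rate is at least that high, so it does not establish 20% per strain. All of this stands, and it is why the loss is stated as conditional.

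Several stronger readings are tempting, and the documents do not support them:

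- **A fixed share of the serologic information is thrown away.** The titers are measured and remain available. The loss applies only to an analysis confined to the cut-off, and only under the assumptions above.
- **The rate is the only HAI analysis planned.** It is the only endpoint defined, but an unspecified humoral analysis is also promised.
- **The cut-off has no standing in myeloma and should be demoted.** The protocol calls it the most accepted measure, and the cited myeloma results are reported at it. That is a good reason to keep the between-arm rate.
- **Section 4 drops the comparison with standard of care.** The Synopsis states it, and the text just before the Section 4 endpoints says the approach is compared directly with standard of care. This is a wording point only.

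**Conclusion.** The concern holds as a gap in the analysis plan. One dichotomy is the only HAI endpoint defined, nothing is specified for the titers or the pre-vaccination value, and the cut-off is stated inconsistently.

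The size is conditional. Under roughly normal log titers with equal SD and a common shift, the information lost is about 31–59% for response rates of 14–50%. The gain in power is material for modest contrasts, small at 20% versus 50%, and possibly nil under a responder-share mechanism. Since the mechanism is unknown, reporting both summaries is safer than relying on either alone.

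This is a secondary endpoint with no stated power, so the primary composite of influenza infection and disease progression is not affected. The mismatch between >40 and 40 or higher rests on the text alone and needs no assumption.

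**What to change.** 1. Keep the between-arm comparison of the seroprotection rate. State one cut-off throughout (>40 or 40 or higher), state that the rate is per strain, and name the visit.
2. Add, per strain, a between-arm comparison of post-booster log2 titer from a linear model with arm, disease-type stratum and pre-vaccination log2 titer. Report it as a geometric mean titer ratio with confidence interval.
3. Set a rule for undetectable titers: half the detection limit, or a censored-normal model.
4. Use as the covariate only samples drawn before the first injection. Appendix A allows that draw up to one week either side of the first vaccine.
5. Word the Section 4 endpoint as a comparison with standard of care, as the Synopsis does.

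The cost is one added secondary analysis and the rule for undetectable titers, with no new sample or assay. This version is dated 31 May 2017, after the end-of-study window of 1–15 May 2016. If the titer analysis is added after unblinding, label it supplementary.
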